6.3 Pharmacokinetic Variables

Refer to PK analysis plan.

6.4 Pharmacodynamic Variables

- Change from baseline in MMP-3 level

- Change from baseline in vascular endothelial growth factor (VEGF) level
- Change from baseline for following variables in lymphocyte subset assays

1. Japan

- CD3+/Lymphocytes (%), CD3+ (cells/uL)
- CD8+/Lymphocytes (%), CD8+ (cells/uL)
- CD4+/Lymphocytes (%), CD4+ (cells/uL)
- CD19+/Lymphocytes (%), CD19+ (cells/uL)
- CD4/CD8 Ratio
- (CD16 or CD56+)/Lymphocytes (%), (CD16 or CD56)+ (cells/uL)
- (CD16+ and CD56+)/CD3- (%), CD16+ and CD56+ (cells/uL)
- (CD16- and CD56+)/CD3- (%), CD16- and CD56+ (cells/uL)
- (CD16+ and CD56-)/CD3- (%), CD16+ and CD56- (cells/uL)
- (CD16- and CD56-)/CD3- (%), CD16- and CD56- (cells/uL)
- CD56 bright/CD3- (%), CD56 bright (cells/uL)
- CD56 dim/CD3- (%), CD56 dim (cells/uL)

2. Korea

- CD3+/Lymphocytes (%), CD3 (cells/uL)
- (CD3+ and CD8+)/CD3+ (%), CD3+ and CD8+ (cells/uL)
- (CD3+ and CD4+)/CD3+ (%), CD3+ and CD4+ (cells/uL)
- (CD16 or CD56+)/CD3- (%), (CD16 or CD56)+ (cells/uL)
- CD19+/CD3- (%), CD19+ (cells/uL)
- CD4/CD8 Ratio
- (CD16+ and CD56+)/CD3- (%), CD16+ and CD56+ (cells/uL)
- (CD16- and CD56+)/CD3- (%), CD16- and CD56+ (cells/uL)
- (CD16+ and CD56-)/CD3- (%), CD16+ and CD56- (cells/uL)
- (CD16- and CD56-)/CD3- (%), CD16- and CD56- (cells/uL)

3. Taiwan

- CD3+/Lymphocytes (%), CD3 (cells/uL)
- (CD3+ and CD8+)/Lymphocytes (%), CD3+ and CD8+ (cells/uL)
- (CD3+ and CD4+)/Lymphocytes (%), CD3+ and CD4+ (cells/uL)
- (CD16 or CD56+)/Lymphocytes (%), (CD16 or CD56)+ (cells/uL)

- CD19+/Lymphocytes (%), CD19+ (cells/uL)
- CD4/CD8 Ratio
- (CD16+ and CD56+)/Lymphocytes (%), CD16+ and CD56+ (cells/uL)
- (CD16- and CD56+)/Lymphocytes (%), CD16- and CD56+ (cells/uL)
- (CD16+ and CD56-)/Lymphocytes (%), CD16+ and CD56- (cells/uL)
- (CD16- and CD56-)/Lymphocytes (%), CD16- and CD56- (cells/uL)

6.5 Other Variables

- Duration of RA (years), calculated as: (Date of Baseline visit – Onset Date of RA +1) / 365.25, and then rounded to one decimal place. The onset date of RA doesn't have the day (e.g., 2013-03), therefore the first day of the month will be used (2013-03-01). Missing onset date of RA will be imputed. For example, if month is missing (e.g., 2013), then the first day of January will be used (2013-01-01).
- Age at onset of RA (years), calculated as: (date of onset of RA – date of birth +1) / 365.25. Missing date of onset of RA will be handled in the same way as described above.
- Duration of exposure (days)
Duration of exposure will be calculated in days, using the following formula:
(‘Date of Last Dose of Study Drug or Reference Drug’* - ‘Date of First Dose of Study Drug or Reference Drug’**) + 1***
* = Max(EX1ENDT, EX2ENDT) [Study Drug and Reference Drug_Dosing-page of the CRF]
** = EX1STDT [Study Drug and Reference Drug_Dosing -page of the CRF]
*** 8 for the Subjects who receive the reference drug
- Overall treatment compliance (during overall treatment period) (%)
In the study, the subjects in the study drug group will be instructed to take 2 tablets once per day, totaling a daily dose of study dose. Therefore, overall treatment compliance will be based on number of tablets and calculated as follows:
$$\text{Treatment compliance in the study drug group (\%)} = \frac{[\text{Total number of tablets actually received in the treatment period}]}{[\text{Total number of tablets planned to receive in the treatment period}]} \times 100$$

where total number of tablets planned to receive in the treatment period = 2 × number of days the subject was in the treatment period (the previous date of Week 52 visit [for completed subjects] / date of withdrawal date [for discontinued subjects] – date of first dose of study drug +1), and total number of tablets actually received in the treatment

period will be calculated as:

(total number of tablets dispensed) – (total number of tablets returned) – (total number of tablets lost).

For the subjects in the reference group, the subjects will receive the reference drug once weekly. Therefore, overall treatment compliance will be based on number of syringes and calculated as follows:

Treatment compliance in the reference group (%) =

$$\frac{[\text{Total number of syringes actually received in the treatment period}]}{[\text{Total number of syringes planned to receive in the treatment period}]} \times 100$$

where total number of syringes planned to receive in the treatment period =

- For complete subjects: $1/7 \times (\text{the date of Week 52 visit*} [\text{for completed subjects}] - \text{the date of first dose of reference drug} + 1)$
- * Week 52 visit is regarded as the final dose at Week 51 + 7
- For discontinued subjects: $1/7 \times (\text{date of withdrawal date} [\text{for discontinued subjects}] - \text{date of first dose of reference drug} + 8)$

and then rounded down to integer number, and total number of syringes actually received in the treatment period will be calculated as:
(total number of syringes dispensed) – (total number of syringes returned) – (total number of syringes lost).

● Treatment compliance during the 12 weeks of study (up to Weeks 12)

Treatment compliance in the study drug group (%) =

$$\frac{[\text{Total number of tablets actually received up to Weeks 12}]}{[\text{Total number of tablets planned to receive up to Weeks 12}]} \times 100$$

where total number of tablets planned to receive up to Weeks 12 = $2 \times$ number of days the subject was during 12 weeks (the previous date of Week 12 visit [for completed Week 12 subjects] / date of withdrawal date [for discontinued before Week 12 subjects] – date of first dose of study drug +1), and total number of tablets actually received up to Weeks 12 will be calculated as:

(total number of tablets dispensed up to Weeks 12) – (total number of tablets returned up to Weeks 12) – (total number of tablets lost up to Weeks 12).

Treatment compliance in the reference group (%) =

$$[\text{Total number of syringes actually received up to Weeks 12}]$$

-----x 100
[Total number of syringes planned to receive up to Weeks 12]

where total number of syringes planned to receive up to Weeks 12 =

- For complete subjects: $1/7 \times (\text{the date of Week 12 visit* [for completed subjects]} - \text{the date of first dose of reference drug} + 1)$
- * Week 12 visit is regarded as the final dose at Week 11 + 7
- For discontinued subjects: $1/7 \times (\text{date of withdrawal date [for discontinued subjects]} - \text{date of first dose of reference drug} + 8)$

and then rounded down to integer number, and total number of syringes actually received up to Weeks 12 will be calculated as:

(total number of syringes dispensed up to Weeks 12) – (total number of syringes returned up to Weeks 12) – (total number of syringes lost up to Weeks 12).

- Number of prior DMARD biologics, calculated as number of unique kinds of DMARD biologics prior to initial dose from following CRF page.
[Concomitant Medication 2B -page of the CRF]
[Biologic DMARD -page of the CRF]
- Prior Biologic DMARD-IR
For the subject whose "Reactivity" checkbox [Biologic DMARD -page of the CRF] is selected as "Inadequate Response" or "Unknown", "Prior Biologic DMARD-IR" is regarded as "Yes", Otherwise "No".

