The reference drug will be subcutaneously administered to subjects once weekly (the last dose will be given at Week 51). The baseline dose should be given at each study center on the day of the baseline visit after all assessments and tests are completed. After the baseline visit, the reference drug will be given taking the same day of the week at baseline as the reference date. The acceptable time range for administration of the reference drug will be within ± 6 days of the reference date, and if the reference drug is given beyond the acceptable time range, it will be regarded as unadministered. The reference drug should also be administered at a minimum of 3-day intervals.

Doses on the day of scheduled visits during treatment with the study drug or reference drug should be given on the day of the visit after all assessments and tests are completed.

The reference drug may be given at any time on administration days (in-hospital administration and self-administration), except those of scheduled visits.

Etanercept can be self-administered only by the subject who has been provided with adequate education and training by the study center and who is judged to be capable of injecting etanercept by himself/herself in the opinion of the investigator/sub-investigator.

The investigator/sub-investigator should instruct subjects who will self-administer etanercept to pay close attention to their condition before and after administration on the day of self-administration to assess the condition in a prompt manner. When the investigator/sub-investigator finds problems with the subject's adherence to self-injection treatment regimens and the mode of administration, the investigator/sub-investigator will administer etanercept at the hospital until the subject can learn to inject it by himself/herself.

The subject's condition before and after in-hospital administration should also be closely monitored.

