5.1.6 Compliance Rules to be Observed by Subjects throughout the Study

The investigator, sub-investigator, or collaborator will explain the following to the subjects during the study period.

- In principle, subjects should visit the study center for the study visit on the specified date. The visits may be adjusted within an allowable range, but the visit dates must be adjusted so that the intervals between the specified visits are 5 weeks at most.
- The subject should visit the study center on the day of each study visit without taking the dose of the study drug for that day prior to the visit. The subject in the reference group should also visit the study center on the day of each scheduled study visit without

- CONFIDENTIAL -

injecting etanercept if he/she has an injection on that visit day. The subject must also fast for at least 8 hours prior to the blood sampling at the time of the study visit. If a subject must make an unscheduled visit due to adverse events, etc., on the day of taking the study drug, the unscheduled visit will be prioritized regardless of whether the study drug was taken and the timing of meals.

- If a new treatment (starting to take a new drug or use a new therapy, etc.) has been prescribed by another department or another medical institution during the study period, the subject should contact the investigator/sub-investigator before starting to use the new treatment, and follow the instructions given by the investigator/sub-investigator. If it is not possible to contact the investigator/sub-investigator in advance, the subject should contact one of them, or the collaborator, as soon as possible.
- Any subject who wishes to take prescription medication or over-the-counter drugs unconfirmed by the investigator/sub-investigator should confirm with the investigator, sub-investigator, or collaborator in advance whether to take the drug. If it is not possible to contact the investigator/sub-investigator in advance, the subject should contact one of them, or the collaborator, as soon as possible.
- Subjects must practice contraception through 2 or more appropriate contraceptive methods throughout the study period, and for 90 days after the end of treatment with the study drug or reference drug in the case of male subjects and for 60 days after the end of treatment with the study drug or reference drug in the case of female subjects of childbearing potential.

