3.2 Study Design

This is a Japanese, Korean and Taiwanese, multi-center, randomized, placebo-controlled, double-blind, parallel-group, confirmatory study to evaluate the efficacy and safety of ASP015K alone or in combination with DMARDs, at doses of 100 mg/day and 150 mg/day, in patients with RA who had an inadequate response to DMARDs. Open-label etanercept will also be administered as the reference drug for 52 weeks (the last dose will be given at Week 51). In the study, ASP015K (test drug) and placebo (comparative drug) will be given as study drugs, and etanercept will be given as a separate reference drug. DMARD response is evaluated at the initiation of screening and then after the screening period, subjects will be randomized in a 1:1:1:2 ratio to the ASP015K 100 mg, ASP015K 150 mg, placebo, or reference groups, and they will receive either the study drug or reference drug for 52 weeks. Subjects in the ASP015K 100 mg, ASP015K 150 mg, and placebo groups will orally receive either ASP015K or placebo once daily after breakfast, while those in the reference group will receive 50 mg of subcutaneous etanercept once weekly.

The planned sample size is 100 subjects each for the ASP015K 100 mg, ASP015K 150 mg, and placebo groups and 200 subjects for the reference group.

Re-screening is allowed only in situations in which a subject underwent the screening procedures (i.e., scans and laboratory work) and owing to logistical circumstances, the allocated time window for these tests has expired. Re-screening is not permitted in cases in which the initial test results do not support eligibility based on inclusion and exclusion criteria. The subject must be classified as a screening failure at that time point.

Based on the consideration of the ethical issues related to long-term placebo use, at Week 12 subjects in the placebo group will be switched to either ASP015K 100 mg or ASP015K 150 mg, and the dosage will be maintained until the end of treatment. The ASP015K dose that will be started for placebo group subjects at Week 12 (100 or 150 mg) will be randomly chosen at baseline. The dose will be switched under the blinded condition.

Subjects in the ASP015K 100 mg, ASP015K 150 mg, or placebo groups who complete this study will be eligible for participation in the open-label extension study (015K-CL-RAJ2). Subjects will make a follow-up visit after the Week 52 visit if they do not enroll into the extension study on the day of the Week 52 visit.

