4 SAMPLE SIZE

One hundred subjects per group will receive the study drug and 200 subjects the reference drug (a total of 500 subjects).

[Rationale for the sample size]

Based on 015K-CL-RAJ1 result and efficacy result from other RA drugs [XELJANZ[®], tablet, 5 mg, CTD (2013)] [CIMZIA, sc, 200 mg, Syringe, CTD (2012)], 62 subjects per group will provide 90% power to detect a difference assumed in the Step 2 in the closed testing procedure (described in Section 7.4.1.1 Primary Analysis) under the following assumptions. In addition, it is assumed that ACR20 response rate of each country (Japan, Korea and Taiwan) is similar.

- ACR20 response rate at Week 12 in the placebo group: 25%
- ACR20 response rate at Week 12 in the ASP015K 100 mg group: 54.5%

- ACR20 response rate at Week 12 in the ASP015K 150 mg group: 65.5%
- Two-sided significance level of 0.05

On the other hand, according to the Extent of Population Exposure to Assess Clinical Safety for Drugs Intended for Long-term Treatment of Non-life-threatening Conditions (PAB/PCD Notification No.592, dated 24 May 1995), ("the long-term treatment guideline"), a sample size of 300-600 subjects under long-term treatment (6 months) is adequate to observe delayed adverse events at a reasonable frequency (generally, 0.5% to 5%) and to observe whether there is an increase in high-frequency adverse events during the later stage of treatment. For treatment lasting 1 year, 100 subjects is acceptable. It is also described in "Guidelines on methodology for clinical assessment of antirheumatic drugs" (PFSB/ELD Notification No. 0217001, dated 17 February 2006) that 100 subjects for 1 year are necessary.

Therefore, to collect data for 300 subjects for 6 month period, and for 100 subjects for 1 year period in both ASP015K 100 mg and 150 mg groups among 015K-CL-RAJ2/RAJ3/RAJ4 studies as long-term treatment data, approximately 80 subjects per treatment group (400 subjects in total) as a target are necessary to be enrolled in Japan. In addition, the target sample size for Taiwan is set at 10 subjects per treatment group (50 subjects in total) as a target in consideration of the requirement of regulatory authority in Taiwan (10% or more Taiwan subjects) and target sample size for Korea is also set at 10 subjects per treatment group (50 subjects in total) as a target. Therefore, the target sample size per treatment group is set at 100 subjects in total for 3 regions.

[Rationale for the sample size for the reference group]

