7.11.5 Handling of Schedule of Assessments of Efficacy Variables

For data obtained after the end of study treatment, the data obtained within + 2 days after the last dose is taken will be included in analysis. For data after the end of reference treatment, data obtained within + 9 days after the last dose will be included in analysis. Baseline for efficacy is defined as value at Day 1 before the first dose of study drug or reference drug for all subjects including placebo assigned subjects. For Week 12/ET, the values at closest date to reference date will be used. As for the subjects who switched to receive ASP015K instead of placebo, the last observation before first dose of ASP015K at Week 12 will be used for the analysis for visit Week 4, 8, 12, 12/ET. For EOT, the closest value to the reference date will be used regardless of the switching from placebo.

- (1) TJC (68 joints)/SJC (66 joints), laboratory test (CRP)

Table 9. Visit Window for TJC (68 joints)/SJC (66 joints), laboratory test (CRP)

Time points defined in analysis	Reference date*	Acceptable time range
Screening**	Day -28 to Day -1	Day -28 to Day -1
Baseline	Day 1	Day 1
Week 4 to Week 48***	Day $7 \times x + 1$	Day $(7 \times x - 6)$ to Day $(7 \times x + 8)$ and before the initiation of treatment with the study drug or reference drug on the visit day
Week 52	Day 365	Day 358 to Day 372
Week 12/ET (Week 12 or at early termination before Week 12)	Day 85	Day 2 to Day 92
EOT (Week 52 or at early termination)	Day 365	Day 2 to Day 372

*: Day 1 represents the first day of study or reference treatment. The day before the initiation of treatment with the study drug or reference drug is expressed as Day -1.

** : PGA, SGA, subject's assessment of pain, and CRP are not applicable.

***: Represents the reference date and acceptable time range for Week x.

- (2) PGA and SGA (VAS), subject's assessment of pain (VAS), HAQ-DI, laboratory test (ESR)

Table 10. Visit Window for PGA and SGA (VAS), subject's assessment of pain (VAS), HAQ-DI, laboratory test (ESR)

Time points defined in analysis	Reference date*	Acceptable time range
Baseline	Day 1	Day 1
Week 4 to Week 48**	Day $7 \times x + 1$	Day $(7 \times x - 6)$ to Day $(7 \times x + 8)$ and before the initiation of treatment with the study drug or reference drug on the visit day
Week 52	Day 365	Day 358 to Day 372
Week 12/ET (Week 12 or at early termination before Week 12)	Day 85	Day 2 to Day 92

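### Exposure bins are cut at visit day numbers and etanercept is credited one day too many, so the same on-schedule 52-week course falls in different bins in the ASP015K and reference arms

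*SAP*

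**What the plan says.** **Exposure formula.** SAP 6.5 defines duration of exposure as the date of last dose minus the "Date of First Dose of Study Drug or Reference Drug’) + 1". A footnote changes the constant to "8 for the Subjects who receive the reference drug".

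**Bins.** SAP 7.3.1 reports counts and percentages per treatment group. Up to Week 12 the limits are 29, 57 and 85 days, with an open top bin from 85. Overall they are 85, 197, 281 and 365 days, with an open top bin from 365.

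**Day numbering.** In SAP 7.11.5, "Day 1 represents the first day of study or reference treatment", and Week x has reference day 7x + 1.

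**End of oral dosing.** The compliance rule in SAP 6.5 ends a completer's treatment period at "the previous date of Week 52 visit [for completed subjects". The Schedule of Assessments has no prescription at Week 52, and protocol 5.1.6 has subjects attend each visit "without taking the dose of the study drug for that day prior to the visit". Protocol 5.1.1 sets a 52-week administration period.

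**End of etanercept dosing.** SAP 3.2: "Open-label etanercept will also be administered as the reference drug for 52 weeks (the last dose will be given at Week 51". The dosing table in protocol 5.1.1 agrees: "the last dose will be given at Week 51".

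**The concern.** The exposure table sets ASP015K beside the reference drug and shows how much of the planned 52 weeks was delivered. Its top bin should hold subjects who received the full course. Two features work against this.

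- The limits are the day numbers of visits. Day 1 is the first dosing day, so the day number of a visit is one more than the number of days dosed before it.
- The two arms are credited differently for the last dose. Plus 1 counts the day of a daily dose. A weekly dose covers that day and six more, which is plus 7. Plus 8 also counts the day on which the next injection would fall due.

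Together these place identical, fully delivered courses on opposite sides of a bin limit. A subject who took every planned ASP015K tablet is then shown short of the final category for a purely arithmetic reason.

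**Working it through.** **1. Where the limits come from.** Applying 7x + 1 to Weeks 4, 8, 12, 28, 40 and 52 gives Days 29, 57, 85, 197, 281 and 365. These are exactly the SAP 7.3.1 limits.

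**2. ASP015K completer on schedule.** The Week 52 visit is on Day 365, so the last planned dose is on Day 364.
Exposure = 364 − 1 + 1 = **364 days**, in the bin from 281 to under 365.

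**3. Etanercept completer on schedule.** The Week 51 dose is on Day 7 × 51 + 1 = 358.
Exposure = 358 − 1 + 8 = **365 days**, in the bin from 365.
Cross-check: doses on Days 1, 8, …, 358 number 52, and 52 × 7 = 364 days covered. With plus 7, 358 − 1 + 7 = 364.

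**4. The other limits.** If the last dose is the one due just before a given visit, the pattern repeats.

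| Visit (week) | 4 | 8 | 12 | 28 | 40 | 52 |
|---|---|---|---|---|---|---|
| ASP015K, days | 28 | 56 | 84 | 196 | 280 | 364 |
| Etanercept with plus 8, days | 29 | 57 | 85 | 197 | 281 | 365 |
| SAP limit | 29 | 57 | 85 | 197 | 281 | 365 |

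**5. With variation in timing.** Assume each permitted day is equally likely. The documents give the windows, not the distribution.
- Oral: the Week 52 visit may fall on Days 358 to 372 (15 days), and exposure is visit day − 1. Reaching 365 needs Days 366 to 372: 7/15 = **47%**.
- Etanercept: the last dose may fall within 6 days of Day 358, that is Days 352 to 364 (13 days), and exposure is dose day + 7. Reaching 365 needs Days 358 to 364: 7/13 = **54%**.

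**6. Effect of the corrections on the overall top bin.**

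| Rule | On-schedule ASP015K | On-schedule etanercept | Even spread, ASP015K | Even spread, etanercept |
|---|---|---|---|---|
| As written (limit 365, plus 8) | 364, below | 365, in | 7/15 = 47% | 7/13 = 54% |
| Limit 364, plus 8 | 364, in | 365, in | 8/15 = 53% | 8/13 = 62% |
| Limit 365, plus 7 | 364, below | 364, below | 7/15 = 47% | 6/13 = 46% |
| Limit 364, plus 7 | 364, in | 364, in | 8/15 = 53% | 7/13 = 54% |

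Moving the limit puts on-schedule completers of both arms where they belong. The plus 7 then removes the one-day difference, which under the even spread is what keeps the two shares apart. Plus 7 alone leaves both arms below the top bin.

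**The case against.** **The plus 8 is a convention, not a slip.** The same pair of constants defines treatment duration in the per-protocol footnote (protocol 7.2.2, SAP 5.2), and plus 8 also enters the planned syringe count for discontinued subjects in SAP 6.5. This stands, and it means that the correction touches more than one line. Repetition does not make the arms comparable, however. For a completer, the syringe denominator (365 − 1 + 1)/7 = 52.14 is rounded down to 52, so an extra day does no harm there. Exposure is not rounded.

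**Other tables limit the damage.** Discontinuations and their reasons (SAP 7.2.1) and compliance (SAP 7.3.2) are tabulated by group, and the exposure summary statistics would show a gap of only one day. This also stands. A reader might infer from the bins that ASP015K patients persist less well, but someone who reads the tables together should not.

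**Complete separation is a boundary case.** A reader might infer that no ASP015K completer and every etanercept completer reaches the top bin. That holds only if every date is exactly nominal, and the documents allow 7 days either way for visits and 6 for injections.

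**The Week 12 table is less certain.** A reader might infer the same fault there, 84 days against 85. That requires exposure to be cut at the last dose before the Week 12 visit (Day 84 oral, Day 78 etanercept). SAP 6.5 defines a single duration and gives no rule for cutting it at Week 12, and subjects who continue are dosed on Day 85 after assessments.

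**The one-year target is a separate matter.** SAP 4 cites guidance: "For treatment lasting 1 year, 100 subjects is acceptable". A reader might infer that the table undercounts towards it. The target is pooled over studies RAJ2, RAJ3 and RAJ4, and neither document says that this table feeds it.

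**Conclusion.** The point holds for the overall exposure table. Under the SAP's own rules, an exactly on-schedule 52-week course counts as 364 days and falls below the top bin in the ASP015K arms, but counts as 365 days and enters it in the etanercept arm. This is a stated rule giving an arm-dependent count, not a missing detail. It rests on the last oral dose being the day before the Week 52 visit, which the compliance rule and the schedule support.

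In practice the distortion depends on how closely sites keep to the nominal dates. It is greatest when they do, and about 7 percentage points (47% against 54%) under the assumed even spread.

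The consequence is confined to descriptive exposure summaries. The primary analysis does not use this variable, and the patient-year rates in SAP 7.5.1.2 run to follow-up or first event. The documents do not support reading it as a threat to the efficacy conclusion or as a shortfall against the one-year exposure target.

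**What to change.** 1. **Main change, SAP 7.3.1.** Set the bin limits to days dosed: 28, 56 and 84 up to Week 12, and 84, 196, 280 and 364 overall.
2. **Second change, SAP 6.5.** Use plus 7 in place of plus 8 for the reference drug, so that both schedules give 364 days for the same course.
3. **Consistency.** Align the plus 8 in the per-protocol footnote (protocol 7.2.2, SAP 5.2), or state why that duration is counted differently. The effect there is one day at the 56-day threshold: a last injection on Day 49 gives 49 − 1 + 8 = 56 and qualifies, but 55 with plus 7. A last injection on Day 50 qualifies either way.
4. **Clarification.** State the date at which exposure is cut for the Week 12 table in subjects who continue treatment.

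The cost is SAP text and table programming. No data collection or trial procedure changes. Because the footnote also stands in the protocol, explaining the difference in the SAP may be simpler than changing both documents.

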5.2 Per Protocol Set (PPS)

PPS includes all subjects of FAS who meet the following criteria. PPS is defined based on the data up to Week 12.

- Have no violation of inclusion criteria;
- Do not meet any exclusion criteria possibly interfering with the efficacy evaluation;
- Receive study or reference treatment for 8 weeks (56 days) or longer from the initiation of treatment to Week 12* (those who have discontinued the study drug or reference drug due to the lack of efficacy should be included in PPS);
- Have study or reference treatment compliance of 75% or higher for 12 weeks after treatment;
- Have evaluable primary efficacy variables; and
- Have no major protocol violations after registration.

Subjects who are considered to have no impact on the efficacy evaluation at the Case Review Meeting will also be included in PPS, if they are not satisfying these criteria.

*: The duration of treatment with the study drug will be calculated by subtracting the first day of study drug treatment from the date of treatment completion plus 1 day, and the duration of treatment with the reference drug will be calculated by subtracting the first day of reference drug treatment from the date of treatment completion plus 8 days.

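### SAP 6.5 miscounts planned etanercept syringes, which distorts reference-arm compliance and can change reference-arm PPS membership

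*SAP*

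**What the plan says.** SAP 6.5 defines reference-group compliance as syringes received (dispensed minus returned minus lost) over syringes planned. The planned number is set as follows.

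- **Completers:** one seventh of (visit date − first dose date + 1), rounded down. The visit date is then replaced. For the first 12 weeks, "Week 12 visit is regarded as the final dose at Week 11 + 7". For the overall period, "Week 52 visit is regarded as the final dose at Week 51 + 7".
- **Discontinued subjects:** one seventh of (withdrawal date − first dose date + 8), rounded down, for both periods.
- **Tablet arms, for contrast:** completers are counted to "the previous date of Week 12 visit [for completed Week 12 subjects", that is, to the day before the actual visit.

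Protocol 5.1.1 keeps injections on the baseline weekday and adds: "The acceptable time range for administration of the reference drug will be within ± 6 days of the reference date". The last dose is at Week 51. The Schedule of Assessments allows the Week 12 and Week 52 visits ±7 days.

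The figure has two uses. SAP 7.3.2 tabulates compliance in bands cut at 50%, 75% and 90%. SAP 5.2 makes it a per-protocol criterion: "Have study or reference treatment compliance of 75% or higher for 12 weeks after treatment". A separate criterion there is "Receive study or reference treatment for 8 weeks (56 days) or longer from the initiation of treatment to Week 12".

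**The concern.** Planned syringes should be the number of weekly doses that fell due in the period, and neither formula delivers that. The formula for discontinued subjects carries an offset one day too large. The formula for completers depends on when the subject happened to take one particular injection, not on the schedule and the visit, and it has no input when that injection was not taken.

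At stake are the accuracy of the etanercept compliance tables and the consistency with which the 75% criterion is applied to reference-arm subjects.

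**Working it through.** **Inputs.** First dose on Day 1; doses due on Days 1, 8, 15, … (Protocol 5.1.1). The Week 11 dose is due on Day 78 and may be given on Days 72 to 84. The Week 51 dose is due on Day 358 and may be given on Days 352 to 364. The PPS threshold is 75%, and the minimum duration is 56 days, with reference duration = last dose − first dose + 8 (SAP 5.2).

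**On-time check.** The SAP states no planned count to reproduce. With on-time dosing its completer formula gives (78 + 7 − 1 + 1)/7 = 85/7, rounded down to 12, and (358 + 7 − 1 + 1)/7 = 365/7, rounded down to 52. Both agree with the schedule.

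**Discontinued subjects, withdrawal on Day w.** SAP count = floor((w − 1 + 8)/7) = floor((w + 7)/7). Doses due by Day w = floor((w − 1)/7) + 1 = floor((w + 6)/7). The two differ, by one, exactly when w is a multiple of 7. Over Days 2 to 91 that is 13 days.

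| Withdrawal day | SAP planned | Due | Taken | SAP score | Score on doses due |
|---|---|---|---|---|---|
| 14 | 21/7 = 3 | 2 | 2 | 66.7% | 100% |
| 28 | 35/7 = 5 | 4 | 4 | 80.0% | 100% |
| 63 | 70/7 = 10 | 9 | 7 | 70.0% | 77.8% |

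In the Day 63 case, with the last dose on Day 57, duration is 57 − 1 + 8 = 64 days. The 56-day criterion is met, and the extra syringe alone causes failure at 75%. The same reversal occurs at Day 56 with 6 taken (6/9 = 66.7% against 6/8 = 75.0%), Day 70 with 8 taken (8/11 = 72.7% against 8/10 = 80.0%) and Day 84 with 9 taken (9/13 = 69.2% against 9/12 = 75.0%). At Day 77 with 9 taken the subject passes either way (9/12 = 75.0%, 9/11 = 81.8%).

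**Completers, Week 11 injection on Day d.** Planned = floor((d + 7)/7).

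| d | Planned | 12 taken | 9 taken | 8 taken |
|---|---|---|---|---|
| 72–76 | 11 | 109.1% | 81.8% | 72.7% |
| 77–83 | 12 | 100% | 75.0% | 66.7% |
| 84 | 13 | 92.3% | 69.2% | 61.5% |

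For Week 51, Days 352–356 give 51, Days 357–363 give 52 and Day 364 gives 53.

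**Week 11 injection missed.** The SAP gives no rule, so the denominator is undefined. If, as an assumption, the last injection taken were substituted, a subject whose last dose was on Day 50 would have floor(57/7) = 8 planned and score 8/8 = 100%, against 8/12 = 66.7% on the schedule. Protocol 3.4.1 permits an interruption of four consecutive doses, and duration would be 50 − 1 + 8 = 57 days, so neither rule would catch this. A tablet subject missing the last 28 of 84 days scores 56/84 = 66.7%.

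**The case against.** Several parts of the opposing case stand.

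- **Late missed doses.** A reader might infer that doses missed after the last injection drop out of the denominator. The SAP does not say so: that needs a fallback to the last injection taken, which is nowhere stated. The supportable point is that no rule exists. A nominal Day 78 reading would fix the count at 12, but subtracting dates and rounding down would then serve no purpose.
- **PPS membership of completers.** It would be too strong to say that membership generally hangs on one injection date. Within the window, only nine doses with the Week 11 injection on Day 84 cross 75%. Eight doses fail and ten or more pass on every permitted day. That 6 of 13 permitted days give a count other than 12 describes dates, not a share of subjects.
- **A constant 12.** This is also wrong. A fully adherent subject seen on Day 78 has had 11 doses before the visit, and one seen on Day 92 has had 13.
- **Early withdrawals.** The Day 14 and Day 28 examples have durations of 15 and 29 days (last doses on Days 8 and 22), so the 56-day criterion already excludes them, unless withdrawal was for lack of efficacy, which SAP 5.2 exempts from that criterion. They bear on the compliance tables. The Day 63 case carries the PPS point.
- **Safeguards.** SAP 7.3.1 and 7.3.2 tabulate suspensions and interruptions separately, and the Case Review Meeting may retain subjects who fail a criterion. Both soften the consequence; neither corrects the count.

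**Conclusion.** The planned-syringe formulas are wrong as written. For discontinued subjects the error is one syringe on every withdrawal day that is a multiple of 7, and it can reverse the 75% criterion for a subject who meets the 56-day rule. For completers the count varies by one either side of the scheduled number with the date of a single permitted injection, and it is undefined if that injection was missed. These results assume only a first dose on Day 1, due dates every seven days, and that the SAP means the actual date of the Week 11 or Week 51 injection. PPS reversals also assume that the other PPS criteria are met.

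The point is minor. A reader might infer that the efficacy conclusions are at risk. They are not: Protocol 7.4 limits the reference group to summary statistics in the primary efficacy analysis, and SAP 7.4.1.1 uses only the two groups being compared in each test. Only etanercept compliance figures and reference-arm PPS membership are affected. The documents do not allow an estimate of how many subjects that would be.

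**What to change.** In SAP 6.5, define planned syringes by weekly due dates:

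- **Week 12 completers:** floor((actual Week 12 visit date − 1 − first dose date)/7) + 1. Visits on Days 78, 85 and 92 give floor(76/7) + 1 = 11, floor(83/7) + 1 = 12 and floor(90/7) + 1 = 13. This matches the day-before-visit basis of the tablet arms and settles the missed Week 11 injection.
- **Overall period, completers:** the same count to the Week 52 visit, capped at 52 because dosing ends at Week 51. Day 365 gives floor(363/7) + 1 = 52; Day 372 gives 53, capped to 52.
- **Discontinued subjects:** floor((withdrawal date − first dose date)/7) + 1, which amounts to replacing the 8 in the present formula by 7.

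Apply these to the compliance tables and to the 75% PPS criterion. A small edge effect remains: a dose taken early just before an early visit can still give one more than planned (visit on Day 78, that day's dose taken on Day 77: 12/11).

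The cost is a few lines of SAP wording and derivation code. Some reference-arm percentages will move, in either direction.
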